When the tracheostomy is no longer needed, the tracheostomy tube is removed; this procedure is known as decannulation. After decannulation the trachostoma will be covered by an external bandage, and the wound will be left to close spontaneously (Figure 1). Airflow will continue to bypass the larynx until the tracheostoma is closed to a level of airtightness. In the meantime, to enable speech and cough function, patients are instructed to apply pressure on the bandage with their fingers (Figure 2). The tracheostoma

[figure not shown]

Figure 1: Open tracheostomy after decannulation.

Figure 2: Neck bandage after decannulation.

usually closes within a few days to weeks. However, surgical closure may become necessary [1]. The surgical approach is complex with a risk of developing subcutaneous emphysema [2]. Decannulation is an important step in the patient's rehabilitation, especially after prolonged mechanical ventilation [3].

Hypothesis

- It is possible to restore/increase airflow in the upper airway with a temporary silicone closure disc immediately after decannulation.
- Cough strength and speech function is significantly improved with the temporary silicone closure disc

Aims

We aim to measure expiration of airflow through mouth and evaluate cough strength and speech on patients with an open versus closed tracheostoma. Closure of the tracheostoma is achieved by insertion of a temporary seal immediately after decannulation.

Method

Population

20 patients from Intensive Care Unit or the Department of Otorhinolaryngology, Head and Neck Surgery at Aarhus University Hospital subjected to tracheostomy decannulation will be included.

Inclusion criteria

- Tracheostomy for minimum 7 days.
- Age > 18 years.
- Capped uncuffed tube size 7 or 8 for at least 24 hours.

Exclusion criteria:

Cognitive dysfunction (patients who are not able to cooperate with investigation)

Day 1.

1. Patients receive oral and written information.

Day 2.

1. Informed consent is obtained.
2. Decannulation will follow standard procedure described in the hospital guideline.

3. Patients will be asked to speak and cough. Spirometry will be performed.
4. Insertion of temporary closure seal “type 1”.
5. Patients will be asked to cough and speak. Spirometry will be performed again.

There will be an option for 2 different degrees of softness: Type 1 “shore 50” and Type 2 “shore 60” (Figure 3).

[figure not shown]

Figure 3: Tracheostomy closed by silicone disc.

Figure 4: Photo of sealing disc with safety thread.

Glottic abnormalities and insertion of the first seal will be evaluated by endoscopic visualization. The endoscopy will be removed before spirometry test with the seal in place. In case of audible signs of insufficient sealing (weak voice and sound from the tracheostoma) seal type 2 will be tested. The rod will be anchored by 2 separate medical clamps outside the neck. See figure 4 and 5. Furthermore, a handheld newton meter will be attached to ensure and measure a constant force on the seal

[figure not shown]

Figure 5: Sealing device with 2 safety clamps.

Number of Patients

To our knowledge, no other study has investigated the consequence of air leakage from a tracheostoma. Therefore, our sample size is based on few other studies on airway physiology related to tracheostomy decannulation. A study from 2002 investigated physiological effects of decannulation in tracheostomized patients with a taped dressing outside the neck; 9 patients were included in that study [4]. Two studies in peak cough flow parametres included 16 and 26 patients, respectively [5, 6]. With reference to these 3 studies, we have chosen to apply for inclusion of 20 patients. When we have conducted tests in 10 patients, we wish to perform an interim analysis to evaluate the significance of differences in airway physiology with open tracheostoma versus closed tracheostoma.

Risks, side effects and disadvantages

The procedure will take place at the specialized treatment room in the Intensive Care Unit, Aarhus University Hospital, where all safety equipment for airway intervention is available and ~~under supervision of~~ specialists in anaesthesiology will supervise. Local anesthesia (xylocain spray) is applied through nose and into the tracheostoma, if the patient requests so. The seal will be sprayed with sterile saline water to minimize friction prior to insertion. [name] (MD, Department of Otorhinolaryngology, Head and Neck Surgery) and [name] (MD, Department of Anaesthesiology and Intensive Care at Aarhus University Hospital) will perform the technical procedure in cooperation. Both physicians have thorough experience with tracheostomy. The patient may experience tickling cough during procedure. The insertion of the temporary closure seal is estimated to last 2 minutes.

Risks for obstruction of the airway is mitigated by clamps and holding string. The seal and rod are made of medical grade silicone. A thread for safety precaution is attached to the seal. The thread will be anchored to a medical clamp before insertion. Total procedure is performed without removal of the clamp. In addition, the rod will be kept in place by a second clamp and manual hold during procedure.

Additionally, design of the seal has taken the risk of airway obstruction into account. The seal dimension takes up max one third of the tracheal lumen. Average cross sectional area of the male adult trachea is approximately $2,8 \text{ cm}^2$. The seal is 1 mm thick and a diameter of 26 mm.

With this dimension the seal will take up maximum 1/3 of the cross section area of the airway. The cross sectional area of a tracheostomy tube size 7 and 8 is 0,865 cm² - 1,11 cm², respectively. While the material is flexible, the material and design ensures that the seal will stay in upright position despite some degree of tensioning from outside the neck. The device has been manufactured by Prolink Sourcing and Trading; a company experienced in manufacturing medical silicone devices.

The seal and tube for insertion will be packed and sterilized locally at Aarhus University Hospital and the procedure will be performed according to standard clinical hygiene precautions and standard handling of tracheostomy.

Spirometry

Having the patient in a relaxed sitting position with both feet flat on the floor, the procedure consist of breathing through a mouthpiece with a nose clamp. Before performing the forced expiration, tidal (normal) breaths can be taken first, then a deep breath taken while still using the mouthpiece, followed by a further quick, full inspiration. Data collected by aspirometry. 1) Forced expiratory volume in 1 s (FEV1). 2)Forced vital capacity (FVC), the maximum amount of air that can be exhaled when blowing out as fast as possible. 3) Vital capacity (VC), the maximum amount of air that can be exhaled when blowing out as fast as possible. 4) FEV1/FVC ratio. 5) Peak expiratory flow (PEF), the maximal flow that can be exhaled when blowing out at a steady rate. 6) Forced expiratory flow, also known as mid-expiratory flow; the rates at 25%, 50% and 75% FVC are given. 7) Spirometry is generally a safe test. Some patients may feel a brief shortness of breath or dizziness after performance of the test.

Upper-airway endoscopy

Endoscopy (nasolaryngoscopy) uses a small flexible telescope. The scope is passed through the nose and into the throat. This is the most common method for examination of the voice box. The patient is awake during the procedure. Numbing medicine will be sprayed into nose and throat on request. This procedure typically takes less than 1 minute.

Endoscopy visualization of the upper airway is standard procedure at decannulation in our Ear Nose and Throat department.

Evaluation of cough and speech

In the newly decannulated patients, cough and speech is challenged (impaired) due to the artificial opening below the glottis. In order to evaluate cough strength, the cough strength scoring tool adopted from Duan et al [7] will be used . The scoring cough pattern ranges from 0 – 5:

- 0= no cough on command
- 1= audible movement of air, but no audible cough
- 2= weakly (barely) audible cough
- 3= clearly audible cough
- 4= stronger cough
- 5= multiple sequential strong coughs.

A similar tool (Likert scale) will be used to evaluate speech function.

Data collection from the patients' medical journal

In order to assess any unforeseen risks for the patients, we will assess the patient medical journal for an overall assessment of inclusion into the study. Furthermore, we will record age, sex, cannulation time, verification of tube capping time, tube size and tube product supplier, neurologic, height and weight.

Information to trial participants

Trial participant will orally and in writing receive detailed information of the study in which they will participate. Written information includes the "Information to trial Participant" and "Your Rights as a trial participant in a biomedical research trial" from the Central Scientific Ethical Committee. A doctor gives the detailed oral information. This is done in closed room and the presence of an observer will be optional. The doctor must ensure that the participant has read and understood the above-mentioned material before the participant signs the trial consent form. Patients will have at least 24 hours of time for reflection before decision. The participants are informed that the consent form may be withdrawn at any time without justification.

Data storage and notification of authorities

All data will be stored and handled in accordance with the legislation on data storage and data security. The participant's data are logged under a participant number, and a participant list is created where consistency between the participant number, participant name, and social security number is documented. The participant list and participant data are archived separately. Data and documents related to the study will be stored for 5 years after completion of the project. The project will be registered in Region Midt internal records of research projects. Within 90 days after the end of the study, the Research Ethics Committee will be notified. The above mentioned authorities will be informed within 15 days if the study for some reason ends sooner than planned.

Ethics

Before the inclusion of project participants the Region Midt Research Ethics Committee must approve the project. The act regarding handling of general data protection regulation and the data protection act will be respected. Participants will receive both written and oral information prior to study entry and it will be highlighted that participation is voluntary.

If trial staff during the trial become aware of the health concerning information that is relevant to the participants, e.g. results from the test, it will not be possible for the participant to refuse this information, as we will not be able to vouch for the consequence of withholding such information. We will inform of this at the information interview, and the participant must agree to these terms to participate in the project.

Potential benefit for the individual patient and future patients overweight the potential small risk for the participating patients. Participating patients will receive enhanced observation, caution and ventilation assess compared to those undergoing normal procedure.

Information to project participants

Potential project participants will orally and in writing receive detailed information of the study the day prior to decannulation. Written information includes the "Information to trial Participant" and "Your Rights as a trial participant in a biomedical research trial" from the Central Scientific Ethical Committee. A doctor gives the detailed oral information. This is done in

closed room and the presence of an observer will be optional. The doctor must ensure that the participant has read and understood the above-mentioned material before the participant signs the trial consent form. The participants are informed that a given consent may be withdrawn at any time without justification and without any consequences for the patient.

Exclusion of participants from the trial / stopping of the trial

Trials Participant may at any time during the study withdraw their consent form. A doctor will address unforeseen side effects or events. Trial participants that do not meet the inclusion criteria will not be included in the trial.

Procedures if a participant leaves the trial

If a trial participant for one reason or another leaves the study is completed a new volunteer will be recruited to replace the discontinued participant. This will be done by the same procedure as the other inclusions. There will be no further follow-up for discontinued participants.

Financing and responsibilities

[name], consultant, is the main supervisor and initiator of the project. [name] and [name] are in charge of the daily management of the project. [name] and [name] will be in charge of the enrolment of participants. [name], [name] and [name] will be in charge of data analyses and dissemination of the results.

An Exploratory pre-seed grant from the Novo Nordisk Foundation has supported (350.000 DKK) the production of a seal suitable for temporary closure test of a tracheostomy immediately after decannulation. The Danish Medicine Agency has been contacted in order to clarify our obligation to notify the tracheostoma sealing disc, which is not a commercial product. The sealing disc has been developed for the purpose of the present study. Generation of data may be useful in a development of a new device for sealing a tracheostomy, however without direct economic benefit from our study. [name] is beside her job as critical care nurse in ICU and project nurse at Comparative Medicine Lab engaged with the development of a new device for tracheostomy.

The patients will be covered by Aarhus University Hospital's patient insurance fund in case of any unforeseen event or side effects originated from the study.

Time-frame

The main time frame of the project will be:

- Inclusion of study participants is intended to begin in June 2019.

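### Does the seal exceed one third of the airway in patients whose trachea is smaller than the male average?

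*Protocol*

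**What the plan says.** All the figures stand in the Protocol under Risks, side effects and disadvantages. The limit appears there twice: "The seal dimension takes up max one third of the tracheal lumen", and after the dimensions, "With this dimension the seal will take up maximum 1/3 of the cross section area of the airway". Between the two statements come the reference lumen ("Average cross sectional area of the male adult trachea is approximately" 2.8 cm²) and the device size ("The seal is 1 mm thick and a diameter of 26 mm"). The tube areas follow: "The cross sectional area of a tracheostomy tube size 7 and 8 is 0,865 cm² - 1,11 cm², respectively". On position, the text says that "the material and design ensures that the seal will stay in upright position despite some degree of tensioning from outside the neck".

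The inclusion criteria ask for age over 18 and a capped uncuffed tube of size 7 or 8. They do not restrict sex or tracheal size. Sex is only a recorded variable ("Furthermore, we will record age, sex, cannulation time").

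**The concern.** A maximum cannot be derived from an average, and the average given is for men only. If the seal filled exactly one third of a 2.8 cm² trachea, every smaller trachea would be filled by more than a third, and many eligible patients, women in particular, could fall in that group.

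The stated size does not produce one third either. The edge of the disc is far below it and the face is far above it. A reader could conclude that the limit was asserted without a basis and holds only for an average man.

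If that were right, the one quantified statement on airway obstruction in the risk section would be too favourable for part of the trial population. Flow measured with the seal in place could also be reduced in those patients, which would touch the outcome.

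**Working it through.** **Inputs, all from the Protocol.** Disc diameter 2.6 cm and thickness 0.1 cm; average male tracheal area 2.8 cm²; tube areas 0.865 cm² (size 7) and 1.11 cm² (size 8); tube size 7 or 8 required for inclusion.

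**1. The stated figure.** One third of 2.8 cm² is 0.933 cm². The dimensions do not give this area:
- edge-on: 2.6 × 0.1 = 0.26 cm², and 0.26/2.8 = 9.3%
- face: π × 1.3² = 5.31 cm², and 5.31/2.8 = 190%
- tube areas against the trachea: 0.865/2.8 = 30.9% and 1.11/2.8 = 39.6%

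The Protocol gives one third as a ceiling. An edge-on share of 9.3% lies under that ceiling and does not contradict it.

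**2. The lumen at which the ceiling would be reached.** Upright, the share is 0.26/A. It equals 1/3 when A = 3 × 0.26 = 0.78 cm².

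**3. Smaller tracheas.** The areas 2.5, 2.0 and 1.5 cm² are assumptions and are not in the Protocol. The last column shows what follows if the seal's own area is taken as 0.933 cm².

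| Lumen A (cm²) | Upright seal, 0.26/A | If 0.933 cm² were occupied |
|---|---|---|
| 2.8 | 9.3% | 33% |
| 2.5 | 10.4% | 37% |
| 2.0 | 13.0% | 47% |
| 1.5 | 17.3% | 62% |

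The last column is what makes the limit appear to fail. Its 0.933 cm² is just the ceiling multiplied by the average lumen. The Protocol does not give it as the seal's area, and step 1 shows that the stated dimensions do not produce it. One cannot both say that the dimensions fail to give one third and use one third as the occupied area.

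**4. The smallest eligible airway.** A lumen that held a size 7 tube is at least as large as the tube. Taking 0.865 cm² as the outer area gives 0.26/0.865 = 30.1%; size 8 gives 0.26/1.11 = 23.4%. The Protocol does not say whether the areas are outer or inner. A circle of 0.865 cm² is 2√(0.865/π) = 1.05 cm across. If the areas were inner, the outer area and hence the smallest lumen would be larger, and the share would be lower.

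**5. The 190% figure.** A round lumen of 2.8 cm² is 2√(2.8/π) = 1.89 cm across. A flat disc 2.6 cm wide cannot lie face-on in it, and no more than 100% of a lumen can be blocked, so 190% is not an occlusion share. The disc must curve to fit. The Protocol calls the material flexible, and bending a 1 mm sheet along the wall does not raise its section above 26 mm × 1 mm.

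**The case for a change.** The strongest counter-argument concerns orientation. If a rigid disc tilts by an angle θ, its projected area is 5.31 sin θ + 0.26 cos θ. At 7° this is 0.905 cm² (32.3% of 2.8 cm²) and at 8° it is 0.996 cm² (35.6%), so the ceiling is passed at about 7.3°. In an assumed 2.0 cm² lumen it is passed at about 4.4°. The Protocol states no tilt limit, gives no test data and allows two softness grades. It says that "a handheld newton meter will be attached to ensure and measure a constant force on the seal" but gives no value for that force. The endoscope is withdrawn before spirometry with the seal in place.

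Part of this stands. The limit depends on the upright position, which is asserted without data, and no calculation is shown. An average male area cannot by itself justify a maximum.

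It does not show that the limit is exceeded. The tilt figures treat a flexible disc as rigid and ignore the tracheal wall, although the disc is wider than the lumen. They show sensitivity to position and do not estimate obstruction. The upright position is the Protocol's stated premise. It comes with a thread anchored to a clamp, a second clamp with manual hold on the rod, and endoscopic evaluation of the first seal's insertion. The Protocol names the clamps and string as the mitigation of obstruction and adds the seal's size as a further point, so the fraction does not carry the safety argument alone.

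The suggested effect on measured flow rests on the percentages in the last column of the table and goes with them. Any flow lost to the seal would also work against the Protocol's hypothesis that closure increases airflow.

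**Conclusion.** The concern does not hold. On the stated dimensions and the stated upright position, the seal takes 9.3% of the average male lumen and about 30% of the smallest lumen that a size 7 tube implies. Both lie below one third, and the limit would fail only under 0.78 cm². The use of a male average does not break it.

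This rests on two assumptions: the disc stays upright, as the Protocol says, and the lumen at the seal is no narrower than the tube it held.

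What remains is an omitted derivation and an upright position stated without data. Writing these out would change no procedure, result or conclusion. Nor is there support for the view that a worked figure would be less favourable, since the one that follows from the dimensions is lower than the ceiling stated.

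### The protocol stops follow-up of every participant who leaves and replaces them, with no safety exception for those in whom insertion of the disc was already attempted

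*Protocol*

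**What the plan says.** Under *Procedures if a participant leaves the trial*, the protocol covers leaving for any reason and sets two rules. The first is that "a new volunteer will be recruited to replace the discontinued participant". The second is "There will be no further follow-up for discontinued participants". Neither depends on why the participant left, or on whether the disc had been inserted.

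Four other statements bear on this:

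- *Exclusion of participants from the trial / stopping of the trial*: consent may be withdrawn at any time, and "A doctor will address unforeseen side effects or events".
- *Financing and responsibilities*: the hospital's patient insurance covers participants "in case of any unforeseen event or side effects originated from the study". The disc is described there as non-commercial and developed for this study.
- *Ethics*: "Participating patients will receive enhanced observation, caution and ventilation assess compared to those undergoing normal procedure".
- *Risks, side effects and disadvantages*: airway obstruction is recognised as a risk, to be mitigated by clamps and a holding string.

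**The concern.** Ending follow-up on discontinuation is harmless for someone who changes their mind before the procedure. It is different for someone who leaves after a purpose-made device has been placed in the trachea. For that patient the protocol does not merely leave safety follow-up open; it rules it out. An analysis plan could not repair this, because it cannot recover data that the protocol says will not be collected.

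At stake is the completeness of what the trial can say about harm. The protocol states that its data may be useful in developing a new sealing device, so an account of what happened to every exposed patient has value beyond this study. Replacement adds to the problem: the place of an exposed patient who left is filled by someone else, and nothing in the protocol says that the first patient is still reported.

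**Working it through.** The protocol states no figure on this point, so there is none to reproduce. The check is mainly a reading of the passages side by side.

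**1. Can a participant leave after exposure?** Yes. Consent may be withdrawn at any time. On Day 2 the seal is inserted at step 4, and step 5 follows with the seal in place: "Patients will be asked to cough and speak. Spirometry will be performed again". A second seal type may be tried if the first does not seal. A patient can stop at any of these points.

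**2. What happens to safety information on that patient?** There are two cases.

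- *An event that makes the patient stop.* It happens in the treatment room before the patient has left the trial, so staff see it. What the rule cuts off is its later course and outcome.
- *An event first appearing after the patient has left.* The rule cuts this off entirely.

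**3. Is there another stated route into the data?** None was found. The sentence on a doctor addressing events concerns care; it says nothing about recording, duration or whether it continues after discontinuation. The insurance sentence concerns cover. *Data collection from the patients' medical journal* uses the journal to assess inclusion and to record descriptive variables, not to look for events after the procedure.

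**4. What do completers get?** The listed schedule ends with the second spirometry on Day 2. No later visit or check is listed for them either. For completers the protocol is silent; for leavers it expressly excludes follow-up.

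**5. Illustration of size.** Inputs: n = 20 from *Number of Patients* ("With reference to these 3 studies, we have chosen to apply for inclusion of 20 patients"). The number of unseen events is assumed, because the protocol gives no event rate. It is also assumed that the leaver is left out of the reported count. The exact (Clopper-Pearson) one-sided 95% upper limit U solves P(X ≤ k | n, U) = 0.05.

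- k = 0, n = 20: U = 1 − 0.05^(1/20) = 0.139, or 13.9%.
- k = 1, n = 21 (20 completers plus one exposed leaver): (1 − U)^21 + 21U(1 − U)^20 = 0.05, so U = 0.207, or 20.7%.

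| Assumed unseen events in replaced leavers | Full data | Rate | Upper limit |
|---|---|---|---|
| 0 | 0/20 | 0% | 13.9% |
| 1 | 1/21 | 4.8% | 20.7% |
| 2 | 2/22 | 9.1% | 25.9% |
| 3 | 3/23 | 13.0% | 30.4% |

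**The case against.** The strongest objection is that leavers lose almost nothing that completers receive. Nothing is scheduled after the Day 2 session for anyone, so deleting the sentence alone would change little. That stands, and it shapes the fix: a follow-up period must be defined for all exposed participants, because tying leavers to the completers' period would tie them to a period that does not exist. It does not excuse an express bar on follow-up after exposure.

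Exposure is also brief: "The insertion of the temporary closure seal is estimated to last 2 minutes". The procedure takes place with airway safety equipment and anaesthesiology supervision. Acute events would be seen at once, and late ones may be few. This stands too, and it limits the weight of the point.

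Several stronger readings are tempting but not supported:

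- *Leavers are the patients most likely to have been harmed.* The protocol gives no reasons for leaving, and a participant may leave before insertion.
- *An event after leaving would never be recorded.* A doctor is to address events, and hospital records may hold them. What is missing is a stated route into the trial's data.
- *The rule contradicts the Ethics section.* The enhanced observation promised there is a comparison with patients having ordinary decannulation, not a promise of follow-up after discontinuation.
- *The rule contradicts the sentence on a doctor addressing events.* Care can continue while trial follow-up ends, so both can be true. The text only fails to say how they fit together.
- *The rule biases a planned safety estimate.* The aims are airflow, cough strength and speech. No safety endpoint or event rate is planned, so no stated estimate is biased.

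The illustration is also open to criticism. It assumes the event whose effect it shows, and its step from 20 to 21 patients comes from the replacement rule as much as from the follow-up rule. It should be read only as showing how far one event moves the limit in a sample of this size.

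**Conclusion.** The point holds in a limited form. The protocol bars further follow-up of every discontinued participant and replaces them, with no safety exception once insertion of the disc has been attempted. The course of an event that led to stopping, or an event that first appears afterwards, has no stated route into the trial's data.

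This rests on the text alone and needs only that a participant can leave after insertion is attempted, which the protocol allows. It does not depend on how many will leave or why. No figure stated in the protocol changes. The move in the upper limit from 13.9% to 20.7% holds only if exactly one such event occurs and goes unreported. The point is worth a short amendment. It is not evidence that harm is likely, or that the protocol's statements on care are false.

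**What to change.** Limit the no-follow-up rule to participants who leave before insertion is attempted. For everyone in whom insertion was attempted, completers and leavers alike, state that:

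- adverse events are recorded over one common period, to be set by the sponsor;
- the outcome of any event present at discontinuation is recorded;
- both apply unless the participant withdraws consent to further data collection;
- exposed participants who leave are reported alongside their replacements.

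Add a clause linking this to the sentence on a doctor addressing unforeseen events, so that it is clear how such an event enters the trial record. Clinical handling of the event need not change.

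The cost is a short amendment, a line in the participant information and a few journal checks. The participant information does need that line: the protocol now describes journal access for inclusion and descriptive data only, so later checks should not be assumed to be covered.
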